## **DATA AND SPECIMEN BANKING**

Participants will be assigned a study ID. The patient identifiers will be stored separately from the coded study data.

Data abstracted from the medical record will be collected on a secure sever, with computers only accessible with passwords. Only the research team will have access to the identified data.

## **SHARING RESULTS WITH PARTICIPANTS**

The results are part of the standard glaucoma care for each participant and they will be discussed with participants as part of the management of the condition.

## **STUDY TIMELINES**

STU00213080

The participant will be in the study for the duration of their office visit (with AS-OCT testing) and surgery. In the context of this research study, participants will also be followed for 12 months after surgery to assess their post-operative course.

It will likely take approximately 12 months to enroll all study participants. The estimated date for completion of primary analyses will be 6 months after enrollment of study.

## **INCLUSION AND EXCLUSION CRITERIA**

### **Inclusion criteria**

- Briefly, the diagnosis of glaucoma is based on the presence of 2 or more of the following findings: 1) glaucomatous optic disc damage, defined as the presence of optic disc excavation, diffuse or focal neuroretinal rim thinning or notching, localized or generalized RNFL thinning; 2) visual field defects consistent with glaucoma; and 3) IOP  $\geq$  22 mmHg.
- Patients with glaucoma who have been advised to undergo TCNR of a failed trabeculectomy bleb by a glaucoma specialist at Northwestern Medicine
- History of failed trabeculectomy (based on clinical features of the trabeculectomy bleb and elevated intraocular pressure)
- Patients can have history of other glaucoma surgery or cataract surgery
- The diagnosis of glaucoma is based on the presence of 2 or more of the following findings: 1) glaucomatous optic disc damage, defined as the presence of optic disc excavation, diffuse or focal neuroretinal rim thinning or notching, localized or generalized RNFL thinning; 2) visual field defects consistent with glaucoma; and 3) IOP  $\geq$  22 mmHg.

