**STUDY ENDPOINTS:**

STU00213080

Results from the following tests obtained as part of this study:

1. Spectralis Anterior-segment OCT (AS-OCT) (Heidelberg Engineering) available in Lavin 15th floor Ophthalmology clinic
2. Digital microscope integrated with Intraoperative OCT (Zeiss Artevo 800, Carl Zeiss Meditec AG) available in the Lavin 11th floor operating room

The primary outcome will be surgical success, defined as a 20% reduction in unmedicated IOP below the pre-operative baseline at the post-operative visits (POD1, POM1, POM3). The success rate will be compared to a cohort of historical controls comprised of a consecutive series of age- and race-matched subjects who underwent TCNR in the operating room by the same surgeon, with the same intraoperative anti-fibrotic therapy, without AS-OCT or iOCT imaging during a five-year time period from 6/1/2015 to 6/1/2020.

The secondary outcomes will be feasibility and utility of intraoperative OCT. Feasibility will be defined as the percentage of cases with successful imaging of the bleb with iOCT. Utility will be defined as the percentage of cases in which iOCT changed surgical decision-making.

Intraoperative OCT will be used to determine whether adhesions have been completely lysed and/or whether further lysis of adhesions is necessary. A survey with set of questions based on prior literature will be used to assess these parameters.

We will also assess whether findings seen with pre-operative AS-OCT can predict what type of blebs will benefit from iOCT-assisted TNCR. Features of AS-OCT and iOCT imaging that will be assessed include quality of image capture, visualization of surgical site, and characteristics of the bleb. Characteristics of the surgical site include bleb height, internal reflectivity, location and number of adhesions, and presence of cysts, cavities, and fistulas.

STU00213080

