**PROCEDURES INVOLVED:**

The devices used in the study are commercially available and have been used extensively in ophthalmology and intraocular surgery. Therefore, no experimental devices will be used. The AS-OCT is routinely obtained and is considered standard of care. The iOCT is commercially available and is also utilized routinely in ophthalmic surgery, particularly for retinal surgery.

The Zeiss Artevo digital microscopy integrated with intraoperative OCT will be used as an adjunct to TCNR. Published research has not shown iOCT to increase risk of complications associated with routine TCNR and we believe injury from imaging is not biologically plausible. Surgery and iOCT will be recorded and saved to a secure NMH server. The surgical videos will only be used for research purposes.

Review of medical records will be performed for patients who agree to participate in the prospective study. Data gathered will include basic demographic information and clinical data relevant to glaucoma management (visual acuity, intraocular pressure, medications, disease

STU00213080

severity). Post-operative course including intraocular pressure, intraoperative or post-operative complications and repeat TCNR or additional surgery will also be collected.

Furthermore, a retrospective review of medical records will be performed for patients who underwent TCNR without iOCT or AS-OCT assistance by the same surgeon during the period from June 1, 2015 to June 1, 2020. This group of patients will serve as historical controls. These individuals will be identified using Enterprise Data Warehouse and billing data. We aim to identify approximately 25 controls. The selection criteria for controls are 1) age within 5 years of each study patient 2) same race as study patient 3) diagnosis of open angle glaucoma and 4) adequate follow up of at least 3 months.

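### Neither arm's criteria address earlier needling of the same bleb or name an index TCNR, so the mix of first and repeat procedures is uncontrolled in the primary comparison

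*Protocol*

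**What the plan says.** **Prospective arm.** Under Inclusion criteria, entry requires "Patients with glaucoma who have been advised to undergo TCNR of a failed trabeculectomy bleb", and "Patients can have history of other glaucoma surgery or cataract surgery". The exclusion nearest to the point concerns corneal or conjunctival pathology beside the bleb that could affect the image. It does not mention needling.

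**Controls.** Procedures Involved gives the source: "These individuals will be identified using Enterprise Data Warehouse and billing data". It then sets out a list of four: "The selection criteria for controls are 1) age within 5 years of each study patient 2) same race as study patient", followed by "3) diagnosis of open angle glaucoma and 4) adequate follow up of at least 3 months". Study Endpoints describes the same group as "a consecutive series of age- and race-matched subjects who underwent TCNR in the operating room by the same surgeon", with the same anti-fibrotic therapy and no OCT imaging, "during a five-year time period from 6/1/2015 to 6/1/2020".

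**Repeat needling.** It appears once, in Procedures Involved, among the post-operative data: "repeat TCNR or additional surgery will also be collected". It is not listed as a baseline characteristic in either arm.

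**Counts.** The Participant Population tables give 25 adults and 25 eyes for each group.

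**The concern.** The primary result is the success rate of about 25 iOCT-assisted procedures set against about 25 historical ones, without randomisation. Comparability rests entirely on how the two sets are chosen. If the chance of success differs between a first and a repeat TCNR of the same bleb, unequal shares of the two kinds produce a difference that has nothing to do with imaging.

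The arms also reach their index procedure by different routes. A prospective patient contributes whichever TCNR has just been advised, which may be a first or a later one. A control comes from a search of five years of records, in which an eye needled twice can appear as two procedures. Someone must choose between them, and the protocol does not say how. Choosing the earlier one tilts the controls towards first procedures, and choosing the later one tilts them towards repeats.

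These are rules on eligibility and control selection. They belong in the protocol and are not analysis detail normally left to an SAP.

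**Working it through.** **1. Is there a rule anywhere?** The protocol states no success rate, effect size or power behind the 25 and 25, so there is no figure to reproduce. The check is a reading of every place where a rule could stand.

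| Place in the protocol | Earlier TCNR of the bleb | Which TCNR is the index | Same patient in both arms |
|---|---|---|---|
| Inclusion criteria | not mentioned | not stated | not stated |
| Exclusion criteria | not mentioned | not stated | not stated |
| Study Endpoints (control definition) | not mentioned | not stated | not stated |
| Procedures Involved (four control criteria) | not mentioned | not stated | not stated |
| Participant Population tables | not mentioned | not stated | separate counts only |

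The tables limit eyes per group. They do not say which procedure of an eye counts.

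**2. How an unequal mix moves the result.** Let *a* and *b* be the shares of repeat TCNR in the iOCT and control arms, and let *p1* and *p2* be the success rates of first and repeat TCNR, with no imaging effect at all. Arm success is share × *p2* + (1 − share) × *p1*, so

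spurious difference (iOCT minus control) = (*b* − *a*) × (*p1* − *p2*).

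All four inputs are assumptions, because the document gives none of them. With *p1* = 60%:

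| Repeat share, iOCT vs control | *p2* = 50% | *p2* = 40% | *p2* = 30% |
|---|---|---|---|
| 20% vs 20% | 0 | 0 | 0 |
| 20% vs 40% | +2 points | +4 points | +6 points |
| 10% vs 50% | +4 points | +8 points | +12 points |
| 40% vs 20% | −2 points | −4 points | −6 points |

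For example, (0.40 − 0.20) × (60 − 40) = +4 points. The sign follows whichever arm has more repeats. With equal shares the effect is zero, as it is if first and repeat procedures succeed equally often.

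**3. Could a patient's own earlier TCNR meet the control criteria?** Race matches automatically. For age, assume that it is compared at surgery, that enrolment starts at the version date of 16 April 2021, and that it lasts the stated 12 months or so. The control window, 1 June 2015 to 1 June 2020, is 1,827 days long.

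- Earliest case, 16 April 2021: own TCNRs from 16 April 2016 qualify, 1,507 / 1,827 = 82% of the window.
- Latest case, 16 April 2022: own TCNRs from 16 April 2017 qualify, 1,142 / 1,827 = 63% of the window.

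The age rule therefore does not prevent it. The earlier TCNR would also have to be in the operating room, by the same surgeon, with the same anti-fibrotic and without OCT.

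**4. Does that earlier TCNR count as a failure?** The window closes 319 days, or about 10 months, before the version date, and about 22 months before the latest assumed case. Success is judged at POD1, POM1 and POM3 only. The gap between the two procedures is therefore at least about 10 months, well beyond the last assessment.

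**5. Were control outcomes already on file?** Three months after 1 June 2020 is 1 September 2020, before the version date. Unless a rule is fixed first, the choice among several TCNRs of one eye can be made with the outcome visible in the chart.

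**The case against.** **Broad entry is a legitimate choice.** Allowing other glaucoma surgery can be read to cover earlier needling, and limiting either arm to first procedures would cost eligible eyes. This stands as an argument against such a limit. It does not close the gap, because on that reading repeats are admitted prospectively and still nothing balances them.

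**The control series is consecutive.** Study Endpoints says so, which narrows discretion over patients. It does not say which TCNR of a patient enters.

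**The arms are plainly meant to be different people.** Consent Process justifies taking no consent from controls on the ground that nothing further will be done to them. The waiver section contrasts participants with the control arm, and the arms are counted separately. This has real weight: overlap is contrary to the sense of the text. It is not an express exclusion.

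**A reader might infer that participants' earlier, unsuccessful needlings will serve as their own controls and depress the control rate.** The documents do not support this. A TCNR repeated at least about 10 months later may well have met the 20% criterion through POM3. Nothing indicates how many such patients exist. If they form part of a consecutive series at their natural frequency, including them is not in itself a distortion.

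**Adjustment could sit in an SAP that is not shown.** That is true of the model. It does not cover the index rule or the control-selection list, which this protocol has already written down.

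**Conclusion.** The gap is confirmed: no rule on earlier needling of the same bleb and no index TCNR in either arm, in a protocol that itself expects repeat TCNR. The primary comparison is therefore open to first-versus-repeat case-mix bias, which age and race matching does not remove.

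The documents do not show that the mix is unequal, only that it is uncontrolled. The bias can favour either arm or be nil, and its size cannot be estimated from the document. The tabulated shifts rest wholly on assumed shares and success rates and show scale, not expectation.

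On overlap, the supported statement is narrow: a patient's own earlier TCNR is not expressly barred from the control set, and whether it failed by POM3 is unknown. No size can be put on that route, since it would need both a count of such patients and their POM3 failure rate, and the document has neither. The point merits a short protocol clarification. It does not show that the comparison is already biased.

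**What to change.** - **Index procedure.** Define the index TCNR by the same rule in both arms, and fix it in writing before any control outcome is read.
- **Recording.** For both arms, take from the chart whether the index is a first or repeat TCNR of that bleb. Earlier needlings before June 2015 should count towards this.
- **Balance.** Add first versus repeat TCNR as a matching factor beside age and race. Where no match exists, adjust for it in the primary comparison.
- **Overlap.** State that no patient is matched to themselves. Report any patient who appears in both arms and handle them in a sensitivity analysis. Silently removing such patients from the controls would delete eyes known to have needed re-needling from one arm only.

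The cost is protocol wording, one extra chart field and a slightly harder match. Restricting entry to first needlings would also remove the imbalance, but it would reduce the number of eligible eyes. That is a trade-off for the sponsor and is not needed to repair this point.

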**BACKGROUND:**

Trabeculectomy is one of the most commonly performed glaucoma procedures performed to control IOP with approximately 18,000 operations performed in US Medicare beneficiaries

STU00213080

alone in 2012. One complication of trabeculectomy surgery is the formation of subconjunctival and episcleral fibrosis, which occurs as part of the wound healing process and can result in fibrosis of the filtering bleb and failure. Transconjunctival needle revision (TCNR) aims to lyse subconjunctival adhesions and reestablish adequate aqueous humor flow from the anterior chamber to the subconjunctival space. One study reported 17% of trabeculectomies require bleb-needling revision. During TCNR the surgeon is able to visualize the trajectory of the needle or blade under the conjunctiva; however, detection of the fibrotic tissue and determination as to whether that tissue has been adequately lysed is difficult, limiting the success rate of the procedure.

Anterior segment optical coherence tomography (AS-OCT) allows for detailed assessment of the internal morphology of the bleb. Studies have utilized AS-OCT to assess morphological features of the bleb and correlate it with surgical success. A small case series reported the utility of AS-OCT for pre-operative planning for bleb revision, in particular, identifying safe access sites and minimizing conjunctival dissection.

More recently, real time OCT integrated with operative microscope has become available. Intraoperative OCT (iOCT) has been utilized extensively in retinal surgery and corneal surgery. Dada et al., described performing iOCT-guided TCNR in 2 patients with failed trabeculectomy blebs without intraoperative or postoperative complications. These authors report they were able to obtain a detailed view of the bleb wall and assess the depth and location of the needle, which permitted better lysis of adhesions. A pilot study by Kumar et al., reported one case of TCNR in which iOCT was used to demonstrate the extent of adhesions and loculations inside the bleb at the beginning of the procedure, and the lysis of these adhesions and formation of large single hyporeflective cavity inside the bleb at the end of the procedure. These small case studies suggest a role of iOCT imaging for TCNR, however, further research is needed to assess its feasibility and utility for routine use.

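### Eyes with other glaucoma or cataract surgery and blebs of any age are eligible, but the rules for choosing historical controls use neither surgical history nor time since trabeculectomy

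*Protocol*

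**What the plan says.** **Who is eligible.** The Protocol's inclusion criteria require "History of failed trabeculectomy (based on clinical features of the trabeculectomy bleb and elevated intraocular pressure") and add that "Patients can have history of other glaucoma surgery or cataract surgery". No limit is placed on the number or type of those operations. Neither the inclusion nor the exclusion criteria set a minimum or maximum time since the trabeculectomy.

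**How controls are chosen.** Two sections govern this.
- Procedures Involved gives a numbered list: "The selection criteria for controls are 1) age within 5 years of each study patient 2) same race as study patient", followed by "diagnosis of open angle glaucoma and 4) adequate follow up of at least 3 months".
- Study Endpoints describes the primary comparison: "The success rate will be compared to a cohort of historical controls comprised of a consecutive series of age- and race-matched subjects". It also requires operating-room TCNR "by the same surgeon, with the same intraoperative anti-fibrotic therapy, without AS-OCT or iOCT imaging", "during a five-year time period from 6/1/2015 to 6/1/2020".

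**What is collected.** For prospective patients, Procedures Involved names demographics, visual acuity, IOP, medications and disease severity. The additional surgery it mentions belongs to the post-operative course. No separate list is given for the controls.

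**What the Protocol says about mechanism.** Background attributes bleb failure to "formation of subconjunctival and episcleral fibrosis, which occurs as part of the wound healing process". Objectives hypothesises that more heavily scarred blebs will benefit from iOCT.

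**The concern.** The primary result is a difference in success rate between patients treated now with imaging and patients treated earlier without it. Nothing is randomised, so any feature of the eyes that changed between the periods and is related to success is carried into that difference.

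Time since trabeculectomy and other surgery in the same eye are natural candidates. The Protocol describes failure as a product of wound healing, which depends on time and on what has been done to the tissue. Scarring itself cannot be compared between the cohorts on imaging, because controls are by definition without AS-OCT. Operation dates and surgical history are chart-based markers that can be sought in both cohorts. Matching on age and race does not stand in for them.

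At stake is whether a difference in success can be attributed to imaging, or reflects a different mix of blebs. The shift could favour either cohort.

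**Working it through.** **1. Eligibility set beside control selection.**

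| Factor | Prospective eyes | Rule for choosing controls |
|---|---|---|
| Age | adults | within 5 years of study patient |
| Race | any | same as study patient |
| Diagnosis | open-angle glaucoma | open-angle glaucoma |
| Follow-up | adequate | at least 3 months |
| Surgeon, anti-fibrotic therapy | reference for matching | same |
| Other glaucoma or cataract surgery | allowed, no limit | not used |
| Time since trabeculectomy | no limit | not used |
| Period | after the control window (protocol dated April 2021) | 6/1/2015 to 6/1/2020 |

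The last three rows carry the point: two factors are open in both cohorts, not aligned between them, and the cohorts come from different years.

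**2. Size of a possible shift.** The Protocol gives no success rates and no prevalence of these factors, so the inputs are assumptions. With no imaging effect:

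shift = (difference between cohorts in the share of affected eyes) × (difference in success between affected and other eyes)

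- Low end: 0.20 × 0.20 = 0.04, or 4 points.
- High end: 0.30 × 0.30 = 0.09, or 9 points.

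Worked example: assume success of 70% in eyes without the factor and 40% in eyes with it, with the factor in 50% of controls and 30% of prospective eyes.
- Controls: 0.50 × 0.40 + 0.50 × 0.70 = 0.55.
- Prospective: 0.30 × 0.40 + 0.70 × 0.70 = 0.61.
- Spurious difference: 6 points.

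**3. Effect on a test in that example.** The Protocol names no test or level; two-sided 5% is assumed. Exact enumeration at 25 against 25 gives the chance of a significant result in favour of imaging when imaging does nothing.
- Pooled z-test: 7.5%, against 3.1% when both cohorts have the factor in 40% of eyes.
- Fisher's exact test: 4.2%, against 1.5%.

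**4. Scale.** At 25 per group the standard error of a difference in proportions is √(2 × p(1 − p)/25). That is 14.1 points at p = 0.5 and 13.0 points at p = 0.7. A shift of 4 to 9 points is therefore less than one standard error.

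**5. What chance alone produces.** For two independent Binomial(25, p) groups with the same prevalence:

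| Prevalence | 5 or more eyes apart (20 points) | 8 or more eyes apart (over 30 points) |
|---|---|---|
| 20% | 0.110 | 0.008 |
| 30% | 0.164 | 0.020 |
| 40% | 0.193 | 0.029 |

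These chance differences are part of ordinary sampling error and are not bias. The shift in step 2 is bias only to the extent that case mix differs systematically between the periods.

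**The case against.** **The control rules already remove some confounding.** Same surgeon, same anti-fibrotic therapy and an operating-room setting all apply, and the therapy bears on scarring. This stands, but none of them aligns bleb age or surgical history.

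**Adjustment may be in a statistical analysis plan that is not shown.** This also stands. A reader might infer that the comparison will ignore these factors; the Protocol supports only that it names no adjustment for them. Choosing controls and abstracting charts are, however, settled in the Protocol, and a later plan cannot adjust for a variable that was never abstracted.

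**The data list may not be exhaustive.** True: it says what data will include, and trabeculectomy history has to be checked for eligibility anyway. The items are unnamed, which does not prove that they will go uncollected.

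**The prognostic premise is not in the Protocol.** A reader might infer from Objectives that scarring governs the result of needling. It says only that more scarred blebs are expected to benefit from iOCT. Nor does the Protocol state that older blebs or eyes with other surgery succeed less often. The factors are plausible confounders, not documented ones.

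**The endpoint is change from each eye's own baseline,** so a stable pressure contribution from an earlier operation is already in that baseline. This is fair, and the point does not rely on such a contribution.

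**Chance imbalance is not bias.** A reader might take the 11% to 19% chance of a 20-point imbalance as evidence of bias. It is sampling error, and the documents give no evidence of a change in case mix over time.

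**Conclusion.** The point holds as a gap in control selection. The Protocol admits eyes with other surgery and blebs of any age, selects controls without reference to either, and does not name them among its baseline items. In a non-randomised comparison across periods, a systematic difference in these factors could be read as an imaging effect.

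Direction and size are unknown. The 4 to 9 points rest wholly on an assumed 20 to 30 point imbalance and an assumed 20 to 30 point difference in success. That is modest beside a standard error of 13 to 14 points, but sampling error is already expressed in the interval and this shift would not be. The documents do not show that such a difference exists. The case for acting is that it could not be examined without the chart items, and that obtaining them is cheap before controls are chosen.

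**What to change.** 1. **Procedures Involved, data collection.** Abstract in both cohorts, for the study eye, the date of the trabeculectomy and the number and type of other glaucoma operations and cataract surgery. Tabulate the balance between cohorts.
2. **Procedures Involved, control selection.** Where more than one chart fits the age and race rule, choose the control blind to outcome: first by the same other-glaucoma-surgery status (none or any), then by nearest time since trabeculectomy.
3. **Study Endpoints.** Reword the description of the controls as a consecutive series to say that matching is done within the consecutive pool; otherwise the tie-break conflicts with it.
4. **Sensitivity analysis.** Repeat the primary comparison in eyes whose only glaucoma operation before TCNR is the trabeculectomy.

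The cost is a few extra chart items per eye and one further analysis. The tie-break excludes no participant, but it helps only where several charts fit, and the Protocol does not give the size of the pool. The restricted analysis will have fewer eyes and a wider interval.
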